## 6.2.1.5. Post-dosing (Day 1)

Subjects will be observed in the clinic for at least 1 hour after dosing. The following procedures will be completed at approximately 1-hour post-dose:

• Review and record adverse events.

Each subject should be reminded to seek medical care and/or contact the Investigator if the subject experiences symptoms of an acute or severe hypersensitivity reaction (eg, shortness of breath, anaphylaxis, urticaria, angioedema) after leaving the clinic.

## 6.2.2. Week 2 Clinic Visit

The following procedures will be performed:

- WOMAC (all subscales).
- Patient's Global Assessment of Osteoarthritis.
- Vital signs after sitting for at least 5 minutes, (blood pressure and heart rate).
- Orthostatic blood pressure (supine/standing) measurement.
- Musculoskeletal physical examination.
- Neurologic exam/Neuropathy Impairment Score (referral for neurological consult if required, refer to Section 7.3.13).
- Concomitant medication review/update.
- Adverse event review.
- Subject daily/weekly IRT entry compliance and data review (daily index joint pain score, weekly non-index joint pain assessment and as applicable, daily rescue medication and weekly NSAID use entries).
- Monitor for violations of concomitant NSAID (outside of oral investigational product) use.

0990777@#39369369888/Approved/Approved On: 06-@tt-2016 14:33 (GMT)

- Review daily and weekly (as applicable) joint pain scores.
- Rescue medication (acetaminophen/paracetamol) compliance review/dispense.
- Oral investigational product (NSAID or matching placebo) compliance review.
- Females of child-bearing potential to be reminded of contraceptive requirements.
- If arthrocentesis will be performed for a subject (refer to Section 7.4.7) and the subject has provided the applicable informed consent, collect synovial fluid, plasma and serum samples for analysis (refer to Sections 7.5.1, 7.5.2, and 7.5.3).

## 6.2.3. Week 4 Clinic Visit

- WOMAC (all subscales).
- Patient's Global Assessment of Osteoarthritis.
- Vital signs after sitting for at least 5 minutes, (blood pressure and heart rate).
- Orthostatic blood pressure (supine/standing) measurement.
- Musculoskeletal physical examination.
- Neurologic exam/Neuropathy Impairment Score (referral for neurological consult if required).
- Lower Extremity Activity Scale (LEAS).
- Concomitant medication review/update.
- Adverse event review.
- Subject daily/weekly IRT entry compliance (daily index joint pain score, weekly non-index joint pain assessment and as applicable, daily rescue medication and weekly NSAID use entries).
- Monitor for violations of concomitant NSAID (outside of oral investigational product) use.
- Review daily and weekly (as applicable) joint pain scores.
- Rescue medication (acetaminophen/paracetamol) compliance review/dispense.
- Oral investigational product (NSAID or matching placebo) compliance review.
- Females of child-bearing potential to be reminded of contraceptive requirements;

099077@#89369&&&ApprovedVApproved On: 06-@ut-2016 14:33 (GMT)

• If arthrocentesis will be performed for a subject (refer to Section 7.4.7) and the subject has provided the applicable informed consent, collect synovial fluid, plasma and serum samples (refer to Sections 7.5.1, 7.5.2 and 7.5.3).

## 6.2.4. Week 8 Clinic Visit

## 6.2.4.1. Pre-dosing

- WOMAC (all subscales).
- Patient's Global Assessment of Osteoarthritis.
- EQ-5D-5L.
- Vital signs after sitting for at least 5 minutes, (blood pressure, and heart rate).
- Orthostatic blood pressure (supine/standing) measurement.
- Musculoskeletal physical examination.
- Neurologic exam/Neuropathy Impairment Score (referral for neurological consult if required).
- Lower Extremity Activity Scale (LEAS).
- Concomitant medication review/update.
- Adverse event review.
- Subject daily/weekly IRT entry compliance (daily index joint pain score, weekly non-index joint pain assessment and as applicable, daily rescue medication and weekly NSAID use entries).
- Monitor for violations of concomitant NSAID (outside of oral investigational product) use.
- Review daily and weekly (as applicable) joint pain scores.
- Rescue medication (acetaminophen/paracetamol) compliance review/dispense.
- Oral investigational product (NSAID or matching placebo) compliance review/dispense.
- Blood samples for PK and PD (NGF) analyses (refer to Section 7.5).
- Blood sample for anti-tanezumab antibody assessment (refer to Section 7.3.14).

- Blood and urine samples for biomarkers (fasting if possible, urine sample should be from 2nd void of the day or after; refer to Section 7.6).
- Urine pregnancy test for females of childbearing potential (must be negative prior to dosing).
- Females of child-bearing potential to be reminded of contraceptive requirements.
- If arthrocentesis will be performed for a subject (refer to Section 7.4.7) and the subject has provided the applicable informed consent, collect a synovial fluid sample (refer to Section 7.5.3).

## 6.2.4.2. Subcutaneous Dosing

Subjects will receive a single injection of blinded, SC investigational product according to the treatment assigned by the IRT system (refer to Section 5).

## 6.2.4.3. Post-dosing

Subjects will be observed in clinic for at least 1 hour after dosing. The following procedures will be completed at approximately 1-hour post-dose:

- Review and record adverse events.
- Sites that are performing actigraphy will provide subjects who completed Baseline activity monitoring (actigraphy) with instructions and an actigraphy device to be used over the course of 14 consecutive days between Week 14 and the Week 16 Visit (refer to Section 7.3.9).

Each subject should be reminded to seek medical care and/or contact the Investigator if the subject experiences symptoms of an acute or severe hypersensitivity reaction (eg, shortness of breath, anaphylaxis, urticaria, angioedema) after leaving the clinic.

## 6.2.5. Week 12 Telephone Contact

- Review/update of concomitant medication and subject daily/weekly IRT entries compliance (daily index joint pain score, weekly non-index joint pain assessment and as applicable, daily rescue medication and weekly NSAID use entries).
- Compliance with oral investigational product (NSAID or matching placebo).
- Monitor for violations of concomitant NSAID (outside of oral investigational product) use.
- Review daily and weekly (as applicable) joint pain scores.
- Rescue medication (acetaminophen / paracetamol) compliance review.

- Adverse events review.
- Females of child-bearing potential to be reminded of contraceptive requirements.
- Sites that are performing actigraphy should remind their subjects to conduct 14 consecutive days of actigraphy between Week 14 and the Week 16 visit.

## 6.2.6. Week 16 Clinic Visit (Primary Efficacy Time Point)

#### 6.2.6.1. Pre-dosing

• Review subject eligibility.

**NOTE:** At the Week 16 visit, subjects must have a 30% or greater reduction in WOMAC Pain subscale relative to Baseline in the index joint and a 15% or greater reduction in WOMAC Pain subscale from Baseline at either Week 2, 4 or 8 in order to continue investigational product. As a risk mitigation measure, subjects who do not meet this efficacy response criteria will be discontinued from the Double-blind Treatment period and enter the 24-week Early Termination Follow-up period (refer to Section 6.4). The efficacy response calculation will be performed by the IRT system.

- Adverse event review.
- WOMAC (all subscales).
- Patient's Global Assessment of Osteoarthritis.
- WPAI:OA.
- EQ-5D-5L.
- TSQM (v.II).
- mPRTI.
- Lower Extremity Activity Scale (LEAS).
- Vital signs after sitting for at least 5 minutes, (blood pressure, and heart rate).
- Orthostatic blood pressure (supine/standing) measurement.
- Musculoskeletal physical examination.
- Neurologic exam/Neuropathy Impairment Score (referral for neurological consult if required).
- Serum and plasma retention samples.

- Clinical laboratory tests (blood chemistry and hematology).
- Blood sample for PK analysis (refer to Section 7.5).
- Blood sample for anti-tanezumab antibody assessment (refer to Section 7.3.14).
- Blood and urine samples for biomarkers (fasting if possible, urine sample should be from 2nd void of the day or after; refer to Section 7.6).
- Urine pregnancy test for females of childbearing potential (must be negative prior to dosing).
- Sites performing activity level monitoring (actigraphy) will collect activity level monitors from subjects.
- Concomitant medication review/update.
- Subject daily/weekly IRT entry compliance (daily index joint pain score, weekly non-index joint pain assessment and as applicable, daily rescue medication and weekly NSAID use entries).
- Instruct subjects that after the Week 16 visit the index joint pain score, non-index joint pain assessment, rescue medication and NSAID use will all be assessed once weekly using IRT (See Section 7.1).
- Monitor for violations of concomitant NSAID (outside of oral investigational product) use.
- Review daily and weekly (as applicable) joint pain scores.
- Rescue medication (acetaminophen/paracetamol) compliance review/dispense.
- Oral investigational product (NSAID or matching placebo) compliance review/dispense.
- Females of child-bearing potential to be reminded of contraceptive requirements.
- If arthrocentesis will be performed for a subject (refer to Section 7.4.7) and the subject has provided the applicable informed consent, collect synovial fluid and serum samples (refer to Sections 7.5.2, 7.5.3).

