**Qualifying Pre-study NSAID Treatment Regimens** 

NSAID	Qualifying Dose Range
Naproxen	440 mg/day* to 1000 mg/day
Celecoxib	200 mg/day (either 100 mg BID or 200 mg QD)
Diclofenac	100 mg/day to 150 mg/day
Aceclofenac	200 mg/day
Loxoprofen	120 mg/day to 180 mg/day
Ibuprofen	1200 mg/day to 3200 mg/day
Meloxicam	5 mg/day to 15 mg/day
Nabumetone	1000 mg/day to 2000 mg/day
Sulindac	200 mg/day to 400 mg/day
Ketoprofen	200 mg/day

\*A minimum dose of 440 mg/day is applicable for naproxen formulations that include the sodium salt of naproxen otherwise the minimum qualifying dose of naproxen is 500 mg/day

The Screening period will include collection of radiographs of the knees, hips, and shoulders (and other major joints exhibiting signs or symptoms suggestive of osteoarthritis) and magnetic resonance imaging (MRIs) of hips and knees. All radiographs will be evaluated by a Central Reader to determine the radiographic eligibility of subjects for the study.

The Double-blind Treatment period ends and the Safety Follow-Up Period begins at the Week 56 visit. Administration of SC investigational product (placebo, tanezumab 2.5 mg or tanezumab 5 mg) will occur during clinic visits at Baseline, Weeks 8, 16, 24, 32, 40 and 48. Subjects will self administer oral investigational product (NSAID or matching placebo) BID from the Baseline visit to Week 56 of the study. At Week 16 in the Double-blind Treatment period, the reduction in WOMAC Pain subscale score from Baseline will be calculated and only subjects meeting pre-defined response criteria may continue in the study. Subjects who do not meet pre-defined response criteria will be discontinued from the Double-blind Treatment period and enter the 24-week Early Termination Follow-up period. At Week 56, subjects will enter the Safety Follow-up period which lasts until Week 80.

Subjects who are discontinued from treatment prior to Week 56, either at their request or at the decision of the investigator, will be required to undergo 24 weeks of follow-up (referred to as Early Termination Follow-Up). The 24 weeks of follow-up will be obtained through 3 clinic visits and monthly phone calls to yield 24-weeks of post-treatment follow-up.

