Tanezumab 2.5 mg, 5 mg, or placebo for tanezumab will be administered as a SC injection and subjects will be observed for adverse events including signs and symptoms of hypersensitivity in the clinic for a minimum of 1 hour after each administration of investigational product. Subjects will take their first oral dose of NSAID (naproxen 500 mg BID, celecoxib 100 mg BID, or diclofenac ER 75 mg BID) or matching placebo of the Double-blind Treatment period in the evening on Day 1 (ie, a morning dose of oral double-blind, investigational product will not be taken). Additional administrations of SC investigational product will occur every 8 weeks following the Baseline (Day 1) administration through Week 48. Oral investigational product (NSAID or matching placebo) will be self-administered by subjects BID through Week 56 of the study. Efficacy, activity level and safety assessments will be conducted during clinic visits between Weeks 2 and 64. In addition, subjects will be contacted by telephone every 8 weeks between Weeks 12 and 60 and every 4 weeks between Weeks 64 and 80 (ie, Weeks 68, 72 and 76).

At the Week 16 visit, subjects must have a 30% or greater reduction in WOMAC Pain subscale relative to Baseline in the index joint and a 15% or greater reduction in WOMAC Pain subscale from Baseline at either Week 2, 4 or 8 in order to continue investigational product. Subjects who do not meet these response criteria will be discontinued from the Treatment Period and enter the 24-week Early Termination Follow-up period.

At Weeks 24, 56, and 80, all subjects will undergo repeat radiographs of each knee, hip and shoulder as well as any additional joint(s) that was imaged at Screening. At Week 24, confirmation of the continuing radiographic eligibility of subjects must be received from the Central Reader prior to administration of the Week 24 SC investigational product. Subjects with Kellgren-Lawrence Grade 3 or 4 osteoarthritis in any knee or hip joint, on the basis of the Central Reader's assessment of the screening X-rays, will have follow-up MRIs of each hip and knee obtained at Weeks 24, 56, and 80.

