Radiographs of each shoulder, knee and hip (and any other major joint imaged at Screening or identified as at risk [refer to Section 7.4.4] during the study) should be performed as soon as possible after the decision to withdraw from the study has been made, provided at least 30 days have passed since the last set of X-rays were collected. Subjects that were determined to have Kellgren-Lawrence Grade 3 or 4 osteoarthritis in any knee or hip joint at Screening should also have an MRI of each knee and hip performed. The remainder of efficacy and safety assessments should be done at the scheduled first visit which is to occur approximately 8 weeks after the last dose of SC investigational product (as described in Section 6.4.1.1). The site should also schedule the subject for two additional clinic visits. The second visit should be scheduled to occur approximately 16 weeks after the subject's last dose of SC investigational product (which corresponds to more than 5 times the elimination half-life of tanezumab) to collect safety and efficacy data (as described in Section 6.4.1.3). Once the clinic visit 16-weeks after the last administration of SC investigational product has been completed and final efficacy assessments have been collected, standard of care treatment will be offered to subjects for the remaining 8 weeks of the required Safety Follow-up period. Standard of care treatment may be initiated as needed and should be recorded on the concomitant medication Case Report Form (CRF). The third and final clinic visit should be scheduled to take place approximately 24-weeks after the subject received the last dose of SC investigational product. That visit (as described in Section 6.4.1.5), will include repeat radiographs of each shoulder, knee and hip (and any other major joint imaged at Screening or identified as at risk during the study) providing at least 30 days have elapsed since the last radiographs were obtained. Subjects that were determined to have Kellgren-Lawrence Grade 3 or 4 osteoarthritis in any knee or hip joint at Screening should also have an MRI of each knee and hip performed. Every effort should be made to have the subject agree to complete the entire 24-week Early Termination Safety Follow-up described above.

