Radiographs of each knee, shoulder and hip (and any other major joint imaged at Screening or identified as at risk during the study) should be performed as soon as possible after the decision to withdraw from the study has been made, provided at least 30 days have passed since the last set of X-rays were collected. Subjects meeting criteria (subjects who had Kellgren-Lawrence Grade 3 or 4 osteoarthritis of any knee or hip at Screening/Baseline, refer to Section 7.3.11) should also be scheduled for magnetic resonance imaging of each hip and knee. The remainder of efficacy and safety assessments should be done at the scheduled first

visit which is to occur approximately 8 weeks after the last dose of SC investigational product (refer to Section 6.4.1.1).

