In the event a subject refuses the Early Termination safety follow-up, or chooses to discontinue during the safety follow-up (after Week 56 and through Week 80), a complete early termination visit should be performed. This early termination visit should include all procedures scheduled for the Week 64 and Week 80 visits unless the Week 64 visit has already been completed, in which case only Week 80 procedures will be required. In addition, if the Week 56 visit was not completed prior to termination, a general physical examination, body weight, WPAI:OA, EQ-5D-5L, TSQM v.II and mPRTI will also be obtained. Subjects will be advised to continue their contraception regimen during a period of 112 days (16 weeks) after the last dose of investigational product.

Subjects entered in the Early Termination Follow-up period will be able to take acetaminophen/paracetamol rescue medication daily up to the Early Termination Follow-up period Visit 2 (which occurs 16 weeks after the last dose of SC investigational product), but will be advised not to exceed the maximal daily dose of 3000 mg. Subjects will be requested not to take acetaminophen/paracetamol (or any other analgesic) in the 24 hours that precede clinic visits at which efficacy assessments are collected (Early Termination Follow-up period Visits 1 and 2, which occur 8 and 16 weeks after the last dose of SC investigational product, respectively). After the second Early Termination Follow-up visit occurring approximately16 weeks after the last SC dose of investigational product, subjects may be started on standard of care treatments for osteoarthritis pain. Subjects may continue to use acetaminophen/paracetamol as needed per local or national labeling.

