Three additional methods will explore the sensitivity of the effect of missing data. The first method of Baseline Observation Carried Forward (BOCF) for missing data at the primary time point of Week 16 will impute the subject's Baseline value for the Week 16 time point, and therefore a zero change from baseline. If a subject's baseline data is also missing then that subject's data remain missing for the post-baseline time point. The second method of Last Observation Carried Forward (LOCF) for missing data at the primary time point of Week 16 will impute the subject's last observed data value for the efficacy endpoint. With LOCF, if a subject is missing all post-baseline efficacy data for a given efficacy endpoint, then baseline will be carried forward (if baseline is missing then the subject would have no contributing data to be included in the analysis). In both the BOCF and LOCF imputation analyses, the same main effects ANCOVA model as described below will be used. The third method will use Mixed Model for Repeated Measurements (MMRM) utilizing all observed data up to and including Week 16, including data considered off-treatment (retrieved dropout; see [Appendix 1.1](#) for details on windows; if multiple observations are within a window, only the single observation selected for analysis by the windowing algorithm will be used in the MMRM analysis).

Analyses of the three co-primary measures at secondary time points will use the BOCF and LOCF imputation methods for missing data, and use the same (main effects) ANCOVA model as described for the primary analyses.

The responder endpoints will be analyzed using logistic regression for binary data, using both BOCF and LOCF separately for missing data of the response endpoint at a particular time point. Imputation using BOCF will lead to the subject being assessed as a non-responder. In addition, in order to closely match the primary imputation analysis, a mixed BOCF/LOCF imputation for response endpoints will be used. In this analysis BOCF imputation (ie, a subject would be a non-responder) would be used for missing data due to discontinuation for reasons of lack of efficacy (Insufficient clinical response on the end of treatment Subject Summary Case Report Form, and also including Patient meets protocol specified pain criteria for discontinuation), adverse event or death up to the time point of interest, and LOCF imputation would be used for missing data for any other reason.

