10. APPENDICES

Appendix 1. DATA DERIVATION DETAILS

Appendix 1.1. Definition and Use of Visit Windows in Reporting

Study visits are planned at Screening, Baseline and then at post-baseline Weeks 2, 4, 8, 16, 24, 32, 40, 48, 56, 64 and 80. If a subject discontinues from the trial then there will be an Early Termination Follow-Up period and for those who refuse, ideally, an Early termination visit. To account for this visit and any early or late scheduled visits (compared to the target study days) we define ‘windows’ to be able to allocate each efficacy observation to a single specific study visit. For the assessments made at each planned study visit (eg, WOMAC subscales, Patient Global Assessment of Osteoarthritis etc.) these visit windows are shown below. When multiple observations occur in a visit window, the observation closest to the protocol specified target day will be used, noting that the latter will be used in the case of a tie.

Visit	Target Study Day	Window
Screening [1]	Variable (up to 37 days prior to baseline visit)	[No lower limit, Day -8]
Baseline	1 (defined as initial day of study drug administration)	[-7,1]
Week 2	15	[2,22]
Week 4	29	[23,43]
Week 8	57	[44,85]
Week 16	113	[86,141]
Week 24	169	[142,197]
Week 32	225	[198, 253]
Week 40	281	[254, 309]
Week 48	337	[310, 365]
Week 56	393	[366, 421]
Week 64	449	[422, 477]

[1] Only efficacy data collected at screening is WOMAC Pain subscale.

One additional window will be created relative to the date of last SC dose for summaries of efficacy data collected beyond the planned treatment period. This window will include data from 16 +/- 4 weeks past the date of the last SC dose. The target day is 113 days after the last SC dose, with a window of [85, 141] days after the last SC dose. If multiple observations occur in this visit window, the observation closest to the specified target day will be used, noting that the latter will be used in the case of a tie.

For the assessments not made at each planned study visit, broader visit windows are shown below. When multiple observations occur in a visit window, the observation closest to the protocol specified target day will be used, noting that the latter will be used in the case of a tie.

LEAS

Visit	Target Study Day	Window
Baseline	1 (defined as initial day of study drug administration)	[-7,1]
Week 4	29	[2,43]
Week 8	57	[44,85]
Week 16	113	[86,141]
Week 24	169	[142,281]
Week 56	393	[282, 477]
Week 80/End of Study	561	[478, no upper limit]

EQ-5D-5L

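### For subjects stopped at Week 16, the SAP's closest-day rule can replace the pre-stop co-primary score with an Early Termination score taken after oral treatment ended

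*Protocol*

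**What the plan says.** **The stopping rule.** Protocol 6.2.6.1 requires a WOMAC Pain reduction of at least 30% at Week 16 and at least 15% at Week 2, 4 or 8. Otherwise "subjects who do not meet this efficacy response criteria will be discontinued from the Double-blind Treatment period" and enter the 24-week Early Termination (ET) follow-up. Protocol Section 3 states the rule as a condition "in order to continue investigational product", which covers the oral product as well as the injection. WOMAC and PGA are collected at this visit before the dosing decision.

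**The next visit.** SC dosing "will occur during clinic visits at Baseline, Weeks 8, 16, 24, 32, 40 and 48" (Protocol Summary, Study Design). A subject stopped at Week 16 was therefore last injected at Week 8. Protocol 6.4 sets the first ET "visit which is to occur approximately 8 weeks after the last dose of SC investigational product". Section 6.4.1.1 lists WOMAC (all subscales) and PGA for it, together with items that the Week 16 visit lacks, such as ECG, body weight, general examination and the autonomic symptom survey. Nothing says that the Week 16 visit serves as ET Visit 1. During ET follow-up, subjects "will be able to take acetaminophen/paracetamol rescue medication daily".

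**The selection rule.** SAP Appendix 1.1 builds the windows partly to accommodate early termination assessments. Where a window holds several scores, the one "closest to the protocol specified target day will be used, noting that the latter will be used in the case of a tie". Visit type has no role in the choice.

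**The concern.** A subject stopped at the Week 16 visit already has an observed score at the primary time point, taken before the stop. A second score a few days later can fall in the same window, and the rule chooses between them on calendar distance alone. Where the ET score wins, the co-primary value describes the subject after oral product was withdrawn.

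That withdrawal is not the same across arms. NSAID subjects lose active drug; tanezumab subjects lose oral placebo, and no injection fell due between the Week 8 dose and the Week 16 visit. The rescue allowance also widens at the stop, from 3 days a week (Protocol 5.9) to daily. A replacement could therefore move the NSAID mean more than the tanezumab means, in a superiority comparison.

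No planned analysis would show it:

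- The on-treatment definition in SAP Section 8 depends only on the SC dose window, and lists Week 16 as on-treatment when the last dose was at Week 8.
- The MMRM does not restore the earlier score, because "only the single observation selected for analysis by the windowing algorithm will be used in the MMRM analysis".
- Multiple imputation, BOCF and LOCF act only on missing values.
- The per-protocol criteria (SAP 5.6.2) do not concern which of two scores is selected.

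**Working it through.** **Inputs.** Target days and windows: SAP Appendix 1.1. Visit windows of ±7 days for Weeks 8 and 16, and dosing visits at least 7 weeks (49 days) apart: Protocol Section 6. ET Visit 1 about 8 weeks (56 days) after the last SC dose: Protocol 6.4.

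**1. The SAP window reproduces.** Target = 7 × 16 + 1 = Day 113. The midpoint to Week 8 is (57 + 113)/2 = 85, so the window opens on Day 86. The midpoint to Week 24 is (113 + 169)/2 = 141. This gives [86, 141], as stated.

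**2. When ET Visit 1 falls due.** Dose on Day 57: 57 + 56 = Day 113. Doses on Days 50 to 64 give Days 106 to 120, always inside the window.

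**3. When the later score wins.** With the Week 16 visit on day w and ET Visit 1 on a later day e, the ET score is kept if |e − 113| ≤ |w − 113|. For w < 113 this means e ≤ 226 − w.

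| Week 16 visit day | ET days that displace it |
|---|---|
| 106 | 107–120 |
| 107 | 108–119 |
| 108 | 109–118 |
| 109 | 110–117 |
| 110 | 111–116 |
| 111 | 112–115 |
| 112 | 113–114 |
| 113–120 | none |

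Displacement is therefore possible on 7 of the 15 permitted days. Days 108 and 113 are at distances 5 and 0, so the ET score is kept. Days 110 and 116 are both at distance 3, so the later (ET) score is kept.

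**4. Illustrative grid.** Take every Week 8 dose day (50–64) with every Week 16 visit day (106–120): 15 × 15 = 225 pairs, of which 197 are at least 49 days apart. Assume ET Visit 1 is exactly 56 days after the Week 8 dose.

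- Due on or before the Week 16 visit: 120 pairs.
- Due after it: 77 pairs.
- Displaces the Week 16 score: 40 pairs, 3 of them ties.
- Gap between visits in those 40: 1 to 7 days, mean 146/40 = 3.65; 20 of the 40 are 3 days or less.

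These are counts of combinations, not probabilities.

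**5. With scheduled-visit precedence.** No Week 16 visit day allows displacement (0 of 15 instead of 7).

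**The case against.** **The second visit may seldom happen.** The Week 16 visit is itself about 8 weeks after the last dose and already covers most of ET Visit 1. A site could add the remaining items on the same day, and the problem then disappears. This stands as a limit on frequency. It is not a safeguard, because no text instructs it.

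**Little may change in so short a gap.** On the grid it is 1 to 7 days. Protocol 5.5.2 advises taking the morning oral dose before the Week 16 visit, WOMAC recalls 48 hours, and Protocol Appendix 3 gives minimum washouts of 2 days for diclofenac and 3 for naproxen and celecoxib. In many cases the later score would still partly reflect NSAID. Protocol 6.4 also asks for no analgesic in the 24 hours before ET Visits 1 and 2, which blunts the rescue difference. These points stand, although PGA asks about today and so gains nothing from the 48-hour recall.

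**Post-stop data may be intended.** SAP Section 8 adopts a modified treatment-policy strategy, and Protocol 9.2.2 admits some early-discontinuation data within 10 weeks of the last dose. Neither says that a post-stop score should displace an observed Week 16 score.

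**Stronger readings to avoid.**

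- A reader might infer that only subjects whose Week 16 score failed have the second assessment, so that a score is discarded because of its own value. The rule also stops subjects on the Week 2/4/8 criterion, and subjects who stop near Week 16 for other reasons also attend ET Visit 1.
- A reader might infer that tanezumab scores cannot move. Protocol 6.4 puts 16 weeks at more than 5 half-lives, so 8 weeks is more than 2.5. Under first-order elimination, less than 2^−2.5 ≈ 18% remains. The direction of bias is plausible, not shown.

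**Conclusion.** The point holds as a defect in the selection rule. The documents allow a pre-stop co-primary score to be replaced by one taken after oral product was stopped, and no planned analysis prevents or reveals it. Replacement needs a Week 16 visit before Day 113 and a separate, later ET Visit 1 no further from Day 113.

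The size is unknown and probably small. A reader might treat 40/197 as a 20% replacement rate and multiply it by assumed inputs: 30–50% of the NSAID arm failing, and WOMAC Pain worsening by 0.5–1.5 points. That gives 0.3 × 0.2 × 0.5 = 0.03 to 0.5 × 0.2 × 1.5 = 0.15 points, against the 0.45 assumed for 2.5 mg in Protocol 9.1. The documents do not support this as an estimate. They give no visit-day distribution, failure rate or post-stop change, and such a worsening is hard to reconcile with a mean gap of 3.65 days. The calculation also sets the tanezumab shift to zero.

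The case for change is that the rule can discard a valid primary observation, possibly with different consequences by arm, and that closing the gap is cheap.

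**What to change.** Before unblinding, add to SAP Appendix 1.1, for WOMAC, PGA and the responder endpoints derived from them:

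- Within a window, the score from the visit scheduled for that window takes precedence.
- An Early Termination or unscheduled score is used only if the scheduled visit has none.
- The closest-day and later-if-tied rules apply only among scores of the same type.

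The cost is one SAP rule and a change to the windowing program. It needs no new data and changes no clinical rule. The MMRM inherits the correction because it uses the same selected record.
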